Study type	Interventional Allocation: randomized Intervention model: parallel assignment Masking: non-blinded Primary purpose: prevention & management Phase IV
Date of first enrolment	Not yet enrolling
Target sample size	154 (77 participants per arm)
Recruitment status	Not yet recruiting
Primary outcome(s)	Long-term care home staff wellness
Key secondary outcomes	Long-term care and retirement home staff burnout, knowledge of, access to and use of wellness supports; SARS-CoV-2 infection; rate of SARS-CoV-2 vaccinations; hospitalizations; and deaths

3. Protocol Version

Issue date: September 07, 2022

Protocol amendment number: 0

Authors: [name], [name], [name], [name], [name], [name]

Evaluating the impact of resource navigators to support long-term care and retirement home staff during and beyond COVID-19

Principal Investigators: Drs. [name] and [name]

Research ethics protocol

Version Dates: Sept 7th, 2022

Version Number: 2

4. Funding

This study is funded by the Canadian Institutes of Health Research (CIHR) – Operating Grant and the University of Toronto Temerty Faculty of Medicine - Knowledge Translation Grant. The educational resources and online repository that will be used for this study were developed through funding from the COVID-19 Immunity Task Force (CITF), the Ontario Ministry of Labour Training and Skills Development (MOLTSD) and the Canadian Immunization Research Network (CIRN).

5. Roles & Responsibilities

5a: Contributorship

(CF) [name], Unity Health Toronto, St. Michael's Hospital, Li Ka Shing Knowledge Institute, [name]

(SES) [name], Unity Health Toronto, St. Michael's Hospital, Li Ka Shing Knowledge Institute, [name]

(SB) [name], Johns Hopkins- Bloomberg School of Health, [name]

(AC) [name], Sunnybrook Health Sciences, [name]

(DH) [name] [name], Division of Occupational Medicine, St Michael's Hospital, [name]

(SM) [name], Division of Infectious Diseases, St. Michael's Hospital, University of Toronto, [name]

(BP) [name], Unity Health Toronto, St. Michael's Hospital, Li Ka Shing Knowledge Institute, [name]

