These barriers were mapped to corresponding implementation strategies via the Behaviour Change Wheel framework to identify education and enablement (e.g., supporting individuals' own self-efficacy) as interventions to mitigate the identified barriers.[13] Utility of these interventions was confirmed by our long-term care home staff partners and the Ontario PSW Association (OPSWA, who support >50,000 members), who believed routine check in calls

Evaluating the impact of resource navigators to support long-term care and retirement home staff during and beyond COVID-19

Principal Investigators: Drs. [name] and [name]

Research ethics protocol

Version Dates: Sept 7th, 2022

Version Number: 2

would reduce social isolation and support PSWs and other long-term care staff to find and use available resources to address their needs.[13]

Through funding from the COVID-19 Immunity Task Force (CITF), the Ontario Ministry of Labour Training and Skills Development (MOLTSD) and the Canadian Immunization Research Network (CIRN), the KTP developed educational resources compiled in a single online repository for long-term care home staff on optimizing infection prevention and control (IPAC) [14-17] in long-term care home, promoting wellness and preventing burnout [18,19] providing ‘wraparound’ [20, 21] resource supports to individuals (e.g., access to food banks, resources on self-isolation, caring for a family member with COVID-19), and addressing SARS-CoV-2 vaccine [22-24] myths and questions (via infographics and town halls created in partnership with OPSWA).[25, 26]

However, currently long-term care and retirement home staff access these resources passively and many do not have the capacity or skills to implement the resources effectively. A navigator is the missing link to putting these resources into practice.

Research Question

Through this clinical trial, we aim to answer the following research question:

What is the impact of tailored 1:1 support from a resource navigator and educational resources (intervention arm) compared to educational resources only (control arm) on the wellness of long-term care and retirement home staff (primary outcome), burnout, knowledge of, access to and use of wellness resources, SARS-CoV-2 vaccination status, self-reported SARS-CoV-2 infection and hospitalization (secondary outcomes).

6b. Choice of Comparators

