Aligning with the findings and work completed to date, a resource navigator for long-term care and retirement home staff was identified as a missing link to putting educational resources into practice. This was selected as our choice of comparator for the purposes of this study and identified needs.

7. Objectives

The aim of this study is to implement and evaluate the impact of implementing resource navigation for long-term care and retirement home staff in enhancing the uptake of available resources. For the purposes of this study, long-term care and retirement home staff will refer to PSWs and other support workers (including those who provide direct resident care or support

Evaluating the impact of resource navigators to support long-term care and retirement home staff during and beyond COVID-19

Principal Investigators: Drs. [name] and [name]

Research ethics protocol

Version Dates: Sept 7th, 2022

Version Number: 2

resident care through ancillary services such as nutrition, housekeeping and laundry) in long-term care and retirement home settings. To achieve our study aim we will:

1. Conduct a trial, which will randomize PSWs and other support service staff to receive 6 months of tailored 1:1 support from a resource navigator and educational resources (intervention arm) versus educational resources only (control arm) to navigate the pandemic.
2. Evaluate the impact of the intervention on PSW's and other support service staff's wellness (primary outcome), burnout, knowledge of, access to and use of wellness resources, alignment of provincial public health guidelines related to SARS-CoV-2 vaccine outcomes, SARS-CoV-2 infection, hospitalization, and death (secondary outcomes).
3. Conduct a process evaluation to assess quality and delivery of the study intervention.

8. Trial Design

This study is designed as a non-blinded, randomized controlled trial with long-term care and retirement home staff with two parallel groups to identify the impact of tailored 1:1 support from a resource navigator and educational resources compared to the use of educational resources only to navigate the SARS-CoV-2 (COVID-19) pandemic and beyond. Randomization will be performed using computer software to generate a 1:1 allocation sequence.

Methods: Participants, Interventions, Outcomes

9. Study Setting

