Principal Investigators: Drs. [name] and [name]

Research ethics protocol

Version Dates: Sept 7th, 2022

Version Number: 2

definition of wellness: “the optimal state of health of individuals and groups. There are two focal concerns: the realization of the fullest potential of an individual physically, psychologically, socially, spiritually, and economically, and the fulfilment of one’s role expectations in the family, community, place of worship, workplace and other settings.” p.5, World Health Organization [32]

The Personal Wellbeing Score is a short, 4-item measure that takes a few minutes to complete. These features increase accessibility and reduce participant burden compared to longer wellness assessment tools. The scale has good internal reliability (Cronbach’s $\alpha = 0.90$) and correlates with health status ($r=0.58$) and health confidence ($r=0.60$). [31] The analysis will use mean Personal Wellbeing Scores of participants and will be conducted at baseline and 6-months post-intervention.

2. Secondary Outcome Measures

Secondary outcome measures will include burnout, knowledge, access to and use of wellness supports, vaccination status, SARS-CoV-2 infection, hospitalization, and death. All measures will be assessed through a baseline and exit survey (at the 6-month time point) that includes the Personal Wellbeing Score.

Burnout will be assessed with the 22-item Maslach Burnout Inventory for Medical Personnel. [33] This measure takes approximately 10 minutes to complete, demonstrates good reliability and validity, has been tested among diverse stakeholder populations including PSWs, and tests for relevant domains (e.g., emotional exhaustion). [33-36] To assess knowledge, access to and use of wellness supports, Likert scale questions directly related to outcomes will be developed.

Demographic information will also be collected, and questions will be developed using the PROGRESS-Plus framework. [37] The PROGRESS-Plus framework will assess characteristics such as place of residence, race/ethnicity/culture/ language, occupation, gender, sex, religion, education, socioeconomic status, and social capital) to determine effects on the study outcomes.

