Via participants’ Ontario Health Insurance Plan (OHIP) number, we will link to the ICES provincial administrative database to obtain participants’ vaccine status, and rates of SARS-CoV-2 infection, hospitalization and death, over the study period. [38, 39]. Unique to the exit survey, study participants will be asked about their satisfaction with the intervention. A process evaluation will be conducted to assess quality and delivery of the study intervention. The resource navigator will track the number, duration and focus of the 1:1 sessions per participant at the end of each individual session using a Process Evaluation- Intervention Tracking Form (Appendix Q). Participant experiences, suggestions for improvement and planning for sustainability will be collected via individual interviews with the resource navigator. A sample of

Evaluating the impact of resource navigators to support long-term care and retirement home staff during and beyond COVID-19

Principal Investigators: Drs. [name] and [name]

Research ethics protocol

Version Dates: Sept 7th, 2022

Version Number: 2

control (n=8-10) and intervention (n=8-10) participants will be interviewed. We will purposively sample the group, with an aim to reflect diversity in gender, age, race and other PROGRESS-plus characteristics

13. Participant Timeline

As noted above, the primary and secondary outcomes will be assessed using a multi-measure baseline and exit survey. Baseline surveys will be conducted 0-30 days after randomization and exit surveys will be conducted at 6 months (182 days) after the randomization date.

Process evaluation data will be collected throughout the duration of the intervention (from 0 days after randomization until the end of intervention (182 days)).

Post-intervention exit interviews will then be conducted at approximately 6-7 months (182-213 days) after the randomization date. These interviews will include a subsample of 8-10 participants from the intervention arm and 8-10 participants from the control arm of the study. See Figure 1 for flow of participants. Note: this will be a rolling recruitment.

Evaluating the impact of resource navigators to support long-term care and retirement home staff during and beyond COVID-19

[figure not shown]
Principal Investigators: Drs. [name] and [name]

Research ethics protocol

Version Dates: Sept 7th, 2022

Version Number: 2

Figure 1. Flow of Participants

14. Sample Size

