Exit Survey	
 • Outcome evaluation • Demographic information 	
 • up to 154 participants (77 per arm) 	
 • At 6 months, Study coordinator and Assistant will collect Exit Survey data after completion of intervention 	
 • Wellbeing • PROGRESS-Plus factors (gender, sex, religion, education, socioeconomic status, and social capital) • Knowledge • Access to supports • Use of wellness supports • Satisfaction with the intervention 	
 • Personal Wellbeing Score (Primary Outcome) • Demographic questionnaire-PROGRESS-Plus Framework and OHIP number (if not collected at baseline) • Maslach Burnout Inventory • Likert scale questions evaluating knowledge, access to and use

Evaluating the impact of resource navigators to support long-term care and retirement home staff during and beyond COVID-19

Principal Investigators: Drs. [name] and [name]

Research ethics protocol

Version Dates: Sept 7th, 2022

Version Number: 2

					of wellness supports
Exit Interview	
 • Outcome evaluation • Process evaluation /Implementation quality 	
 • 8-10 participants from intervention arm • 8-10 participants from control arm 	
 • At 6-7 months, Research coordinator will collect interview feedback post intervention 	
 • Barriers and facilitators • Wellbeing • Participant experiences • Suggestions for improvement • Planning for sustainability • Implementation quality 	
 • Interview questions
ICES provincial administrative database	
 • Outcome evaluation 	
 • up to 154 participants (77 per arm) (data linkage using OHIP#) 	
 • At 6-7 months, Study coordinator and Assistant will use OHIP number to link administrative data 	
 • Vaccine status • Rates of SARS-CoV-2 infection • Hospitalization • Death 	
 • ICES provincial administrative database fields

18b. Retention

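### Vaccination and the ICES events are not anchored to each participant's randomisation, so earlier doses (and, on a literal reading, earlier infections and hospitalizations) dilute the arm comparison

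*Combined protocol and SAP*

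**What the plan says.** The vaccination outcome appears under three names. Objective 2 in Section 7 lists "alignment of provincial public health guidelines related to SARS-CoV-2 vaccine outcomes". The registration data set in Section 2b lists "rate of SARS-CoV-2 vaccinations". Section 12 lists "vaccination status, SARS-CoV-2 infection, hospitalization, and death", and the linkage paragraph and Table 1 also speak of vaccine status. No section gives a rule for alignment: which doses, which guideline version, which reference date.

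The data source also varies. The research question in Section 6a has "SARS-CoV-2 vaccination status, self-reported SARS-CoV-2 infection and hospitalization (secondary outcomes". Section 12 says "All measures will be assessed through a baseline and exit survey (at the 6-month time point", and its linkage paragraph then takes "vaccine status, and rates of SARS-CoV-2 infection, hospitalization and death, over the study period" from ICES. Table 1 says "Study coordinator and Assistant will use OHIP number to link administrative data" at 6-7 months, and lists no vaccination or infection item for either survey.

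On timing, Section 13 dates the surveys, process data and exit interviews from randomisation, and adds "Note: this will be a rolling recruitment". It gives no start or end for the ICES outcomes. Section 10 does not exclude people who are already vaccinated. Section 20a plans t-tests between arms, with no baseline vaccination term, at-risk set or person-time.

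**The concern.** A record of vaccine status at 6-7 months includes every dose received before the participant was randomised. Someone who was up to date at entry and does not fall due again contributes the same value in either arm, whatever the navigator does. The larger that group, the smaller the arm difference.

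The event outcomes raise a related problem. Under rolling recruitment, a fixed calendar period contains time before later participants were randomised. Infections and hospitalizations in that time cannot be affected by the navigator. Counting them pulls the ratio between arms towards 1 and adds noise.

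A flat result on these outcomes could then be read as showing that navigation does not change vaccination or infection, when much of what was counted came before navigation began. Two analysts could also follow the plan faithfully, choose different windows, and report different results.

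**Working it through.** **The plan's own figure.** The only sample size concerns the primary outcome. With effect size 0.5, two-sided 5% and 80% power, the exact t-test needs 63.77, so 64 per arm; 64 × 1.2 = 76.8, so 77 per arm. This reproduces. No figure is given for any vaccination or ICES outcome, so the rest is illustration at 77 per arm. That number is an upper limit, because linkage depends on participants supplying an OHIP number.

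**Vaccination, nobody falling due after entry.** Assumed: a share q up to date at randomisation; uptake among the rest 30% (control) v 60% (navigation).

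Difference in end status = (1 − q) × (0.60 − 0.30).

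| q | Status difference | Power, status in everyone | Power, new doses among those due |
|---|---|---|---|
| 70% | 0.30 × 30 = 9 points | 33% | 55% |
| 80% | 0.20 × 30 = 6 points | 22% | 38% |
| 90% | 0.10 × 30 = 3 points | 11% | 20% |

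Powers are simulated t-tests, good to a point or two. With uptake of 20% v 40% instead, q = 80% gives a 4-point difference and power of 11% v 22%.

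**Vaccination, some falling due during follow-up.** Keep q = 80% and 30% v 60%, and assume that half of those up to date at entry fall due by day 182.
- Share due at any time = 0.20 + 0.80 × 0.5 = 0.60.
- End status: control 0.40 + 0.60 × 0.30 = 0.58; navigation 0.40 + 0.60 × 0.60 = 0.76; difference 18 points.
- Simulated power: about 68% for status in everyone; about 40% for new doses only among those due at entry (77 × 0.20 = 15.4 per arm); about 84% for new doses among all who are or fall due (77 × 0.60 = 46.2 per arm).

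So dilution is smaller when people fall due later, and the choice of at-risk group matters more.

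**Events.** Assumed: constant hazard, 6 months after randomisation, m earlier months counted.

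Apparent ratio = (m + 6 × RR) / (m + 6). For RR = 0.70:
- m = 1: (1 + 4.2) / 7 = 0.74
- m = 2: (2 + 4.2) / 8 = 0.78
- m = 3: (3 + 4.2) / 9 = 0.80

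The range for m comes from the Timeline table, which puts assignment in June-July 2022. A two-month enrolment span gives up to 2 earlier months and about 1 on average. The version dated 7 September 2022 says enrolment had not begun, so a period counted from June would hold about three months before anyone was randomised.

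As a risk, with 20% v 10% over 6 months and 2 earlier months at the control rate: earlier risk = 1 − 0.8^(2/6) = 0.072; control 1 − 0.928 × 0.8 = 0.257; navigation 1 − 0.928 × 0.9 = 0.165. The risk ratio moves from 0.50 to 0.64, and power from 41% to 29%.

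**The case against.** **The window may already be per participant.** Everything else in Section 13 runs from randomisation, and Table 1 gives the linkage the same 6-7 month label as the exit interviews, which are timed that way. This stands as a fair reading. A reader might infer that earlier infections and hospitalizations will be counted; the documents do not say so. They leave the window undefined. The point cannot apply to death, which cannot precede randomisation.

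**The objective could still be answered.** A reader might infer that guideline alignment is not measured at all. That goes too far: ICES vaccine data could supply it. What is missing is the rule.

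**There is no bias.** Randomisation balances earlier doses and events on average, and a 6-point difference is a valid estimate of the effect on end coverage in all staff. This stands. It is not, however, the effect among people whom the navigator could still influence, and it is imprecise.

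**The vaccination dilution may be small.** If status means being up to date, people can lapse during follow-up, and the assumption that nobody falls due is extreme. This also stands. It rules out restricting the analysis to those due at entry, which would drop people who fall due later and could be less powerful than status in everyone (40% v 68% above). It does not remove the need to define the outcome.

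**Conclusion.** The concern holds in this form: vaccination is a cumulative status at a single linkage, compared without adjustment, and the ICES window has no start tied to randomisation. The consequence is dilution and lost precision in secondary outcomes. The primary outcome and the sample size are untouched.

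The size depends on rates that the documents do not give. The 6-point figure requires 80% up to date at entry, no one falling due later and 30% v 60% uptake; if half of those up to date fall due, the difference is 18 points. The 0.74 to 0.80 range requires a calendar reading, a constant hazard and one to three earlier months.

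This should be settled before linkage, so that the window is not chosen after the data are seen.

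**What to change.** Change Sections 7 and 12, Table 1 and the registry entry together.

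1. **Events.** Count infection, hospitalization and death from each participant's randomisation to day 182, using linked dates.
2. **Vaccination.** Define the outcome as receipt of a guideline-due dose between randomisation and day 182, among all participants who are due at randomisation or fall due by day 182. Determine who is due from pre-randomisation dose dates only, so that the group cannot depend on arm, and name the guideline version and its date. Alternatively, analyse end status in everyone, adjusted for vaccine status at randomisation. Report unadjusted end status as description only.
3. **Name and source.** Use one outcome name in place of alignment, rate and status. Name one source per outcome, reconciling self-report (Section 6a) and survey (Section 12) with the ICES linkage (Section 12 and Table 1).

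The cost is wording, plus date fields in the ICES request already budgeted at $35,000, assuming that the linked records carry dates. No new visit or survey is needed. The vaccination analysis may use fewer participants, and power stays low in most of the scenarios above. The gain is an estimate that answers Objective 2, not a well-powered test.
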